#### 4.4.3. Other Efficacy Variables

Other efficacy endpoints include:

- Proportion of patients with SCORAD-50 ( $\geq 50\%$  reduction in SCORAD from baseline) response at week 16
- Proportion of patients with SCORAD-75 ( $\geq 75\%$  reduction in SCORAD from baseline) response at week 16
- Proportion of patients with SCORAD-90 ( $\geq 90\%$  reduction in SCORAD from baseline) response at week 16
- Patient global assessment of disease: proportion of patients with no symptom and proportion of patients with no symptom or mild symptoms at week 16
- Patient global assessment of treatment: proportion of patients who rate their eczema symptoms as “much better” at week 16
- Pruritus categorical scale: proportion of patients who achieve absence of pruritus or mild pruritus at week 16
- Proportion of patients who achieve reduction of IGA score by  $\geq 2$  from baseline to week 16
- Change in ACQ-5 score from baseline at week 16
- Change in weekly averaged TNSS score from baseline at week 16
- Change from baseline to week 16 in GISS (erythema, infiltration/papulation, excoriations, lichenification)
- Number of missed school days assessment during the treatment period
- Mean score of injection site pain as assessed by visual analogue scale for all visits through week 16

#### Patient Global Assessment of Disease

Patients will rate their disease based on a 5-point Likert scale. Patients will be asked: “Overall, how would you rate your eczema symptoms right now?” Response choices are:

- 1: No symptoms
- 2: Mild symptoms
- 3: Moderate symptoms
- 4: Severe symptoms
- 5: Very severe symptoms

Patients will undergo this assessment at time points according to [Appendix 10.2](#).

### PatientGlobalAssessmentofTreatment

Patients will rate their satisfaction with the study treatment based on a 5-point Likert scale. Patients will be asked: “Compared to before you started the study, how would you rate your eczema symptoms now?” Response choices are:

- 1: Much better
- 2: A little better
- 3: No difference
- 4: A little worse
- 5: Much worse

Patients will undergo this assessment at time points according to [Appendix 10.2](#).

### PatientAssessmentofPruritusUsingPruritusCategoricalScale(PCS)

The pruritus categorical scale is a 4-point scale used to assess symptoms that has been used in clinical studies of AD and has less of a “middling” effect ([Kaufmann 2006](#)). The scale is rated as follows:

- 0: Absence of pruritus
- 1: Mild, pruritus (occasional slight itching/scratching)
- 2: Moderate pruritus (constant or intermittent itching/scratching that does not disturb sleep)
- 3: Severe pruritus (bothersome itching/scratching that disturbs sleep).

Patients will be instructed on using the patient diary to record their pruritus categorical scale score at the baseline visit. Patients will complete the rating scale DAILY throughout the entire study (screening period, treatment period, and follow-up period). Clinical sites will check and remind patient to complete the diary at each visit.

For each day, if there are multiple PCS scores collected on the same day, the maximum (worst) of all the scores collected will be chosen. For each week, calculate round prorated average of collected scores for Category Score. For example, if there are 3 scores in a week, the prorated average = (score1 + score2 + score3)/3 round to 1.0.

The baseline PCS is defined as the round prorated average of the PCSs reported right before and on the baseline visit (i.e. study day -6 to day 1).

### JuniperAsthmaControlQuestionnaire(ACQ-5)

The 5-question (symptoms only) version of the Juniper ACQ is a validated questionnaire to evaluate asthma control. The questionnaire will be administered only to the subset of patients with a medical history of asthma and who fluently speak a language in which the questionnaire is presented (based on availability of validated translations in participating countries), at time points according to [Appendix 10.2](#).

The ACQ-5 has 5 questions, reflecting the top-scoring five asthma symptoms: woken at night by symptoms, wake in the mornings with symptoms, limitation of daily activities, shortness of breath and wheeze. Patients are asked to recall how their asthma has been during the previous week and to respond to the symptom questions on a 7-point scale (0 = no impairment, 6 = maximum impairment). A global score is calculated: the questions are equally weighted and the ACQ-5 score is the mean of the 5 questions and, therefore, between 0 (totally controlled) and 6 (severely uncontrolled). Higher score indicates lower asthma control. On the 7-point scale of the ACQ-5, a change or difference in score of 0.5 is the smallest that can be considered clinically important, corresponding to the Minimal Clinically Important Difference (MCID) defined by the developer.

Based on the manual of ACQ, any more than one missing value is not acceptable. If more than one of the questions have missing value, the global score is invalid and will be considered as missing. If only one question has missing value, it will be interpolated (pro-rated) using the completed questionnaires from the previous visit. If the questionnaire from the previous visit is not complete either, the missing value will be imputed as the average of the completed questions within the current visit.

#### Global Individual Signs Score (GISS)

Individual components of the AD lesions (erythema, infiltration/papulation, excoriations, and lichenification) will be rated globally by the Investigator (i.e., each assessed for the whole body, not by anatomical region) on a 4-point scale (0 = none, 1 = mild, 2 = moderate, and 3 = severe) using the EASI severity grading criteria. The cumulative score is the sum of the four components, which will be ranged from 0 to 12. The GISS will be assessed at the scheduled and unscheduled clinic visits according to [Appendix 10.2](#).

#### Total Nasal Symptom Score

The Total Nasal Symptoms score (TNSS) will be used to assess the effect of study drug on symptoms of allergic rhinitis. The TNSS total score will be the sum of the following 5 symptoms: rhinorrhea, nasal congestion, nasal itching, sneezing, and difficulty in sleeping, each rated on a 0 to 3 scale of severity. The modified TNSS total score will be the sum of 4 symptoms: rhinorrhea, nasal congestion, nasal itching, and sneezing. Both TNSS total score and modified total score will be analyzed. The questionnaire will be administered only to the subset of patients with allergic rhinitis who fluently speak a language in which the questionnaire is presented (based on availability of translations in participating countries). Patients will be instructed on using the patient diary to record their TNSS score at the scheduled and unscheduled clinic visits according to [Appendix 10.2](#).

The weekly averaged TNSS score will be calculated as the prorated average of the reported daily TNSS score within 7 days prior to the visit. For example, if there are 3 scores in a week, the prorated average = (score1 + score2 + score3)/3.

Subgroup analysis of TNSS data for patients with perennial allergic rhinitis may be performed.

### InjectionSitePainVisualAnalogueScale

Patients will be asked to provide an assessment of pain experienced during injection of study drug using a Visual Analogue Scale (VAS). This assessment will be performed after injection of the study drug at certain in-clinic visits according to Section 6.1.

## **4.5. Safety Variables**

### **4.5.1. Adverse Events and Serious Adverse Events Variables**

Adverse events and serious adverse events will be collected from the time of informed consent signature and then at each visit until the end of the study. All adverse events are to be coded to a “Preferred Term (PT)”, “High Level Term (HLT)” and associated primary “System Organ Class (SOC)” according to the Medical Dictionary for Regulatory Activities (MedDRA, latest version).

An **Adverse Event** is any untoward medical occurrence in a patient administered a study drug which may or may not have a causal relationship with the study drug. Therefore, an AE is any unfavorable and unintended sign (including abnormal laboratory finding), symptom, or disease which is temporally associated with the use of a study drug, whether or not considered related to the study drug.

AEs also include: any worsening (i.e., any clinically significant change in frequency and/or intensity) of a pre-existing condition that is temporally associated with the use of the study drug; abnormal laboratory findings considered by the investigator to be clinically significant; and any untoward medical occurrence.

A **Serious Adverse Event** is any untoward medical occurrence that at any dose results in death; is life-threatening; requires in-patient hospitalization or prolongation of existing hospitalization; results in persistent or significant disability/ incapacity; is a congenital anomaly/ birth defect; or is an important medical event.

The criteria for determining whether an abnormal laboratory, vital sign or ECG finding should be reported as an AE are as follows:

- Test result is associated with accompanying symptoms, and/or
- Test result requires additional diagnostic testing or medical/surgical intervention, and/or
- Test result leads to a change in dosing (outside of protocol-stipulated dose adjustments) or discontinuation from the study, significant additional concomitant drug treatment, or other therapy

The pre-treatment period is defined as the period from the patient providing informed consent up to the first dose of study drug. The treatment emergent period is defined as the period from the administration of first study dose to the EOS visit.

The pre-treatment AE and treatment emergent AE (TEAE) are defined as following:

- Pre-treatment signs and symptoms (Pre-treatment AEs) are AEs that developed or worsened in severity during pre-treatment period.
- Treatment-emergent AEs (TEAEs) are AEs that developed or worsened in severity compared to the baseline during the treatment and follow-up period. As only the worsening pre-existing AEs and new AEs reported during the treatment and follow-up period will be collected in the study, all AEs collected during the treatment and follow-up period are considered as TEAEs.
- TEAEs during the 16 week treatment period are AEs with onset after the first dose up to the week 16 visit date (study day 113 if the week 16 visit date is missing), or early termination visit whichever is earlier. TEAEs that have an onset during the 16 week treatment period and continued afterwards into follow-up period will be counted only once as TEAEs during the 16 week treatment period.
- TEAEs during the Follow-up period are AEs with onset after the week 16 visit date up to the end of study.

Adverse event of special interest (AESI) category:

- Anaphylactic reactions
- Systemic or severe hypersensitivity reactions
- Malignancy (except in situ carcinoma of the cervix, non-metastatic squamous or basal cell carcinoma of the skin)
- Helminthic infections
- Suicide-related events
- Any type of conjunctivitis or blepharitis (severe or serious)
- Keratitis (any event regardless of severity or seriousness)

[Appendix 10.54](#) provides a list of AESIs search criteria.

#### 4.5.2. Laboratory Safety Variables

Hematology, chemistry, urinalysis, and pregnancy testing samples will be analyzed by a central laboratory.

Samples for laboratory testing will be collected according to visit schedule ([Appendix 10.2](#)).

Tests will include:

##### Serum Chemistry

Sodium	Total protein, serum	Total bilirubin 
Potassium	Creatinine	Total cholesterol 
Chloride	Blood urea nitrogen (BUN)	Triglycerides
Carbon dioxide	AST	Uric acid
Calcium	ALT	CPK 
Glucose	Alkaline phosphatase	
Albumin	Lactate dehydrogenase (LDH)	

1 Direct and indirect bilirubin will be measured when the total bilirubin is above the ULN

2 Low-density lipoprotein and high-density lipoprotein

3 CPK isoenzymes will be measured when CPK >5× the ULN

##### Hematology

Hemoglobin	Differential:
Hematocrit	Neutrophils
Red blood cells (RBCs)	Lymphocytes
White blood cells (WBCs)	Monocytes
Red cell indices	Basophils
Platelet count	Eosinophils

##### Urinalysis

Color	Glucose	RBC
Clarity	Blood	Hyaline and other casts
pH	Bilirubin	Bacteria
Specific gravity	Leukocyte esterase	Epithelial cells
Ketones	Nitrite	Crystals
Protein	WBC	Yeast

##### Other Laboratory Tests

Serum and urine pregnancy testing will be performed for all female patients of childbearing potential at time points according to [Appendix 10.2](#). The following tests will be performed at screening: HIV, HBsAg, HBsAb, HBcAb, Hepatitis C antibody, tuberculosis (will be performed on a country-by-country basis according to local guidelines if required by regulatory authorities or ethics boards), and alcohol and drug screen test.

#### **4.5.3. Vital Sign Variables**

The following vital signs parameters will be collected:

- Respiratory rate (bpm)
- Heart rate (beats/min)
- Sitting systolic and diastolic blood pressures (mmHg)
- Body temperature (°C)

Vital signs including temperature, sitting blood pressure, heart rate, and respiration, will be collected predose at every in-clinic visit. At the first 3 administrations of study drug (day 1, week 2 and week 4), sitting blood pressure, heart rate, and respiratory rate will also be assessed at 30 ( $\pm$ 10) minutes postdose. See [Appendix 10.2](#) for assessment time points.

#### **4.5.4. Body Weight and Height**

Body weight and height will be measured at time points according to [Appendix 10.2](#).

#### **4.5.5. Physical Examination Variables**

The physical examination variable values are dichotomized to normal and abnormal. A thorough and complete physical examination will be performed at time points according to visit schedule ([Appendix 10.2](#)).

#### **4.6. Pharmacokinetic (PK) Variables**

Serum samples for measuring functional dupilumab concentrations will be collected at time points according to [Appendix 10.2](#). PK variables consist of functional dupilumab concentration and time (both actual and nominal).

#### **4.7. Antibody (ADA) Variable**

Serum samples for anti-dupilumab antibody will be collected at time points according to visit schedule ([Appendix 10.2](#)).

ADA variables include ADA response status and titer as follows:

- Total patients with preexisting immunoreactivity  
Pre-existing immunoreactivity defined as either an ADA positive response in the assay at baseline with all post first dose ADA results negative, OR a positive response at baseline with all post first dose ADA responses less than 4-fold over baseline titer levels

- Total patients with treatment emergent response  
Treatment emergent response is defined as a positive response in the ADA assay post first dose when baseline results are negative or missing. The treatment emergent responses will be further characterized as Persistent, Indeterminate or Transient
  - Persistent Response - Treatment emergent ADA positive response with two or more consecutive ADA positive sampling time points separated by greater than 12-week period (greater than 84 days), with no ADA negative samples in between
  - Indeterminate Response - as a treatment-emergent response with only the last collected sample positive in the ADA assay
  - Transient Response - a treatment emergent ADA positive assay response that is not considered persistent or indeterminate.
- Total patients with treatment boosted response  
Treatment boosted response defined as a positive response in the ADA assay post first dose that is greater than or equal to 4-fold over baseline titer levels, when baseline results are positive
- Titer Values (Titer value category)
  - Low (titer <1,000)
  - Moderate ( $1,000 \leq \text{titer} \leq 10,000$ )
  - High (titer >10,000)

Samples positive in the ADA assay will be further characterized for ADA titers and for the presence of neutralizing antibody (NAb) response.

Total patients positive in the Neutralizing antibody assay  
Treatment-emergent or treatment boosted ADA positive patients that are positive in the NAb assay at any time point analyzed.

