- Revise the list of AESIs. The list of AESIs has been revised across the dupilumab program in AD and incorporates the data gathered from adult phase 3 studies, the dupilumab risk profile, and regulatory feedback. This will enable focus of pharmacovigilance activities on identified and potential risks with this drug.
- Revise the Biomarker Procedures section to align with the new procedures for collection, use, and storage of biomarker serum and plasma samples [REDACTED]
- Revise the definition of concomitant medications and procedures
- Delete the section on Cytochrome P450. Data became available recently from a phase 1 study to examine the Effects of Dupilumab on the Pharmacokinetics of Selected Cytochrome P450 Substrates in Adult Patients with Moderate to Severe Atopic Dermatitis. The results of this study showed no evidence for a clinically meaningful effect of dupilumab on the PK of a cocktail of prototypic substrates, indicating that blockade of IL4/13 signaling does not have a clinically relevant effect on the activity of CYP3A, CYP2C19, CYP2C9, CYP1A2 or CYP2D6, in adult patients with moderate to severe AD.
- Revise the definition of "total number of patients with treatment-emergent ADA response in ADA assay" from "total number of patients with treatment-emergent ADA response in ADA assay – defined as either a positive response in ADA assay postbaseline when baseline results are negative, or any postbaseline positive response in ADA assay with a titer  $\geq 4$ -fold over the baseline titer level." to "total patients with treatment-emergent response – defined as a positive response in the ADA assay post first dose when baseline results are negative or missing". This change was made to harmonize with the definition used for ADA analysis performed in phase 3 adult studies.

- Revise the definition of “persistent ADA response” from “a treatment-emergent ADA positive response with 2 or more consecutive positives in the ADA assay separated by at least a 12-week period” to “a treatment-emergent ADA positive response with 2 or more consecutive ADA positive sampling time points, separated by greater than a 12-week period (with no ADA negative samples in between)”. This change was made to harmonize with the definition used for ADA analysis performed in phase 3 adult studies.

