**6.2.4.2. Anti-Drug Antibody Measurements and Samples**

Serum samples for ADA assessment will be collected at time points listed in section [6.1](#).

Long term follow-up of patients who are ADA positive at their last study visit (early termination or end of study) and who do not participate in the open-label extension study may be considered based on the overall clinical presentation at that time.

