### 8.4. Anti-Drug Antibody Variables

Anti-drug (dupilumab) antibody variables include status (positive or negative) and titer as follows:

- Total number of patients negative in ADA assay at all time
- Total number of patients positive in ADA assay at any time
- Total number of patients with preexisting immunoreactivity – defined as either an ADA positive response in the assay at baseline with all postbaseline ADA results negative, or a positive response at baseline with all postbaseline ADA titer  $< 4$ -fold over baseline titer level
- Total patients with treatment-emergent response – defined as a positive response in the ADA assay post first dose when baseline results are negative or missing.
- The treatment-emergent responses will be further characterized into the following categories:
  - Persistent ADA response – a treatment-emergent ADA positive response with 2 or more consecutive ADA positive sampling time points, separated by  $> 12$ -week period (with no ADA negative samples in between)
  - Transient ADA response – a treatment-emergent ADA positive response that is not considered persistent or indeterminate

- Indeterminate ADA response – a treatment-emergent ADA positive response with only the last collected sample positive in the ADA assay
- Total patients with treatment boosted response - defined as a positive response in the ADA assay post first dose that is greater than or equal to 4-fold over baseline titer levels, when baseline results are positive
- Titer value category
  - Low (titer <1,000)
  - Moderate ( $1,000 \leq \text{titer} \leq 10,000$ )
  - High (titer >10,000)

Anti-drug antibody positive samples will be further characterized for the presence of neutralizing antibody (NAb) response

- Total patients positive in the NAb assay at the time points analyzed

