### **3.4. The ADA Analysis Set (AAS)**

The ADA analysis set will consist of all patients who received any study drug and who had at least one non-missing ADA result after first dose of the study drug. Patients will be analyzed according to the treatment actually received.

The neutralizing antibody (NAb) Analysis Set (NAS) will consist of all patients who received any study drug and who had at least one non-missing Nab result or who had all samples negative in the ADA assay after first dose of the study drug. Patients will be analyzed according to the treatment actually received.

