## **5.10. Analysis of Immunogenicity Data**

### **5.10.1. Analysis of ADA Data**

The incidence of ADA variables described in Section 4.7 will be summarized using absolute occurrence (n) and percent of patients (%) with pre-existing immunoreactivity, treatment-emergent, treatment-boostered, persistent ADA responses and titer categories by treatment groups. Listing of all ADA peak titer levels will be provided for ADA positive subjects.

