### 5.11.2. Immunogenicity and Safety and Efficacy

Associations between the ADA response and safety events may be explored.

Associations between the ADA variables and key efficacy endpoints may be explored for the dupilumab treated group. Plots of efficacy variables may be analyzed for potential impact of treatment-emergent ADA on efficacy.

The above mentioned safety and efficacy analyses will be conducted using the following ADA response categories:

- ADA positive patients, that is patients with treatment-emergent or treatment-boosted response,
- ADA negative patients, that is patients with pre-existing immunoreactivity or negative in the ADA assay at all time points
  
- Patients with persistent ADA response,
- NAb positive patients, that is patients who had positive in the NAb assay at any time point analyzed.
- Peak post-baseline titer level in treatment emergent or treatment boosted ADA positive patients:
  - High,
  - Moderate,
  - Low

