### **6.1. Definition of Baseline for Efficacy/Safety Variables**

Unless otherwise specified, the baseline assessment of the study for all measurements will be the latest available valid measurement taken prior to the first administration of study drug. If any randomized patients are not treated, the baseline will be the last value on or prior to the randomization. The baseline of NRS is defined in Section 4.4.2.

The following rules specify the determination of baseline by both date/time information:

1. For the AE, lab, PK and ADA data, both date and time of the measurement will be used to determine baseline by comparing with the first injection date and time.
2. For other data except AE, lab, PK or ADA, only date of the measurement will be used to determine baseline by comparing with the first injection date.

For the rescreened patients, all data from the same patient will be used to derive baseline regardless if the data is from the screen-failure subject ID or enrolled subject ID.

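### The persistent-ADA rule needs more than 84 days, but planned samples are exactly 84 days apart, so some patients with no observed negative are classed as Transient

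*SAP*

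**What the plan says.** SAP 4.7 divides treatment-emergent ADA responses (baseline negative or missing) into three classes.

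- Persistent: at least two successive "ADA positive sampling time points separated by greater than 12-week period (greater than 84 days), with no ADA negative samples in between" are required.
- Indeterminate: only the last collected sample is positive.
- Transient: everything else.

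Protocol 8.4 has the same rule: "a treatment-emergent ADA positive response with 2 or more consecutive ADA positive sampling time points", more than 12 weeks apart. The Protocol's Amendment 1 log gives the reason for this limit: "This change was made to harmonize with the definition used for ADA analysis performed in phase 3 adult studies".

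The schedules of events (Protocol 6.1; SAP 10.2) place ADA samples at day 1, week 4, week 16 and week 28, and at unscheduled and early termination visits. Protocol 5.8 offers OLE screening at week 16 to everyone who completes treatment. Under Protocol 3.1 and the Table 2 footnote in both documents, only those who decline the OLE are followed to week 28. Protocol 6.2.4.2 allows longer follow-up of patients who are antibody-positive at their last visit, but only for those "who do not participate in the open-label extension study may be considered based on the overall clinical presentation at that time".

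The ADA analysis set (SAP 3.4) is "all patients who received any study drug and who had at least one non-missing ADA result after first dose of the study drug", so patients who roll over stay in the denominator. SAP 5.10.1 summarises the SAP 4.7 variables, including "persistent ADA responses and titer categories by treatment groups". SAP 5.11.2 lists persistent response among the groups for exploratory work: "safety and efficacy analyses will be conducted using the following ADA response categories".

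**The concern.** The limit is strict, and it equals the planned distance between neighbouring post-dose samples. A patient who enters the OLE at week 16 can reach Persistent only if the two visits happen to fall at least 85 days apart. Otherwise the residual definition makes the patient Transient, a label that suggests the response went away. Nothing in that patient's data shows this, since every sample from week 4 onward was positive.

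The label then reflects two things that are not antibody behaviour: whether the patient accepted the OLE, and whether a visit fell a day early or late. What is at stake is how the persistent and transient figures by arm are read, and the composition of one exploratory group in SAP 5.11.2. The split into ADA-positive and ADA-negative, the titer categories and neutralising antibody status do not use persistence.

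**Working it through.** **Inputs.** Limit: more than 84 days (SAP 4.7). Target days: week 4 = 29, week 16 = 113, week 28 = 197. Windows: ±3 days at weeks 4 and 16, ±4 at week 28 (schedules of events).

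**Plan's own figure.** 12 weeks × 7 = 84 days, as SAP 4.7 states.

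**Gaps between samples**

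| Pair | On schedule | Within windows |
|---|---|---|
| Week 4 to 16 | 113 − 29 = 84 | 110 − 32 = 78 to 116 − 26 = 90 |
| Week 16 to 28 | 197 − 113 = 84 | 193 − 116 = 77 to 201 − 110 = 91 |
| Week 4 to 28 | 197 − 29 = 168 | 193 − 32 = 161 to 201 − 26 = 175 |

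**Classification under SAP 4.7.** Take a treatment-emergent patient who is positive at weeks 4 and 16, rolls over, and has a span of 84 days or less.

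- Not Persistent: the span is not above 84.
- Not Indeterminate: more than the last sample is positive.
- Hence Transient, the residual class.

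If followed and positive at week 28, the same patient spans at least 161 days from first to last positive and is always Persistent. A followed patient first positive at week 16 and still positive at week 28 is back at the 84-day limit.

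**Chance that the gap exceeds 84 days.** The documents do not describe visit scatter, so its shape is assumed.

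- Nominal days: 0% for either neighbouring pair.
- Independent uniform whole days, week 4 to 16: 7 of 49 combinations give exactly 84, so P = (49 − 7)/2 ÷ 49 = 21/49 = 42.9%.
- Same assumption, week 16 to 28: 28/63 = 44.4%.
- Rounded normal scatter centred on target (SD 0.5 to 2 days), week 4 to 16: 24% to 42%.
- Same normal scatter with week 16 shifted by one day: about 3% (early) to 76% (late), both extremes at SD 0.5.

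**Dependence on OLE uptake.** Among patients positive at every sample from week 4, let f be the share who roll over (not in the documents, so 0 to 100%) and q the chance that the week 4 to 16 gap exceeds 84. The share labelled Persistent is (1 − f) + f × q.

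| f | q = 3/7 (actual dates, uniform) | q = 0 (nominal days) |
|---|---|---|
| 0% | 100% | 100% |
| 25% | 85.7% | 75% |
| 50% | 71.4% | 50% |
| 75% | 57.1% | 25% |
| 90% | 48.6% | 10% |
| 100% | 42.9% | 0% |

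**Would changing the sign be enough?** No. With 84 days or more, the week 4 to 16 pair qualifies in (21 + 7)/49 = 57.1% of combinations on actual dates.

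**The case against.** **The consequence is small.** Persistent response is one descriptive count and percentage, and the associations in SAP 5.11 are optional. This stands, and it is why the point is minor.

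**The definition is deliberate.** It was harmonised with the adult phase 3 studies. This also stands, as a reason to keep it. It does not justify calling a patient with no observed negative Transient.

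**The date convention is clear enough.** A limit written in days most naturally means actual dates, and the condition of no negatives between most naturally means first to last positive. SAP 6.1 points the same way: "For the AE, lab, PK and ADA data, both date and time of the measurement will be used to determine baseline". That rule concerns baseline only, however. The natural reading is probably the intended one, but it is not stated, and on actual dates the boundary remains.

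**Later samples may exist.** Unscheduled and early termination visits carry an ADA sample. SAP 2.3 also still has roll-over text that keeps patients to week 28 by default, or requires an early termination visit at or after week 16. Some roll-over patients could gain a later sample under that text. It conflicts with Protocol 5.8 and with the SAP's own Table 2 footnote, and an early termination visit held at week 16 adds no span.

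**A stronger reading.** A reader might infer that the persistent percentage is biased low. That holds only against sustained positivity that nobody observes after roll-over. The rule as written is applied exactly, and sparse sampling can also push upward, because a negative between weeks 4 and 16 would go unseen.

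**Conclusion.** The point holds as a minor flaw in classification and reporting. The rule places some patients with uninterrupted observed positivity in Transient, and the persistent/transient split by arm depends partly on OLE uptake and visit timing. The classification and the day ranges follow from the documents alone. The percentages rest on assumed scatter and on reading the span as first to last positive.

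The number of patients affected cannot be stated, because the documents give neither OLE uptake nor ADA incidence. A reader might also infer that the comparison between arms is distorted. That would need uptake or visit timing to differ by arm, which is possible but not shown. No efficacy endpoint, alpha or power is touched.

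**What to change.** Keep the limit of more than 84 days.

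- **SAP 4.7, dates.** State that actual sampling dates are used and that the span runs from first to last positive with no negative between.
- **SAP 4.7, category.** Add *persistence not assessable*: treatment-emergent patients with two or more consecutive positives through the last available sample and a span of 84 days or less. Exclude them from Transient. This covers both the week 4 to 16 and the week 16 to 28 pairs, and extends the reasoning behind Indeterminate, where follow-up also ends on a positive.
- **SAP 5.10.1.** Show this category as a row, and give per arm the number of patients with a week-28 ADA sample.
- **Sensitivity summary.** Repeat the classification by nominal visit with a limit of 12 weeks or more. Every patient positive at two neighbouring scheduled samples from week 4 onward then counts as persistent, whatever the scatter.

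The cost is a few sentences and table rows before database lock, with no new patients, visits or samples. The table will have one more category than the adult tables. A one-day boundary remains between Persistent and not assessable, which the sensitivity summary addresses.
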